### **3.4 End of study**

The end of the study as a whole will be reached as soon as the last visit of the last subject has been reached in all centers in all participating countries (EU and non-EU).

### **3.5 Primary completion**

The primary completion event for this study is the last visit within the 7-year follow-up (or follow-up as defined in the feeder trial protocols) after last dose of radium-223 dichloride or placebo for the last remaining subject in this study for all centers in the respective country.

The primary completion date for this study according to the FDA Amendment Act is specified in a separate document (not part of this study protocol).

## 4. Study population

### 4.1 Inclusion criteria

Eligible subjects must meet the inclusion criteria listed below:

1. Subject was previously enrolled in a selected company-sponsored feeder trial, and has received at least 1 dose of radium-223 dichloride or placebo in the feeder trial.
2. Written informed consent.

### 4.2 Exclusion criteria

Not applicable to this follow-up study.

### 4.3 Justification of selection criteria

The selection criteria in this study are consistent with the ethical standards used in studies of oncology drugs, and are appropriate for the long-term safety evaluation of subjects from the feeder trials.

## 4.4 Withdrawal of subjects from study

### 4.4.1 Withdrawal

*Section modified by Amendment 1 (Section 13.1).*

#### Withdrawal criteria

Subjects *may* be withdrawn from study if the following reason occurs:

- At the specific request of the sponsor and in liaison with the investigator (e.g., obvious non-compliance, inability to provide medical information).

Subjects *will* be withdrawn from the study for the following reasons:

- Withdrawal of consent: At their own request or at the request of their legally acceptable representative. At any time during the study and without giving reasons, a subject may withdraw consent and decline to participate further in the study. The subject will not suffer any disadvantage as a result. The subject will continue to be followed up until they complete the procedure for withdrawal of consent specified in this section.
- Lost to follow-up (i.e., the subject is not able to be contacted for 2 consecutive 6-month interval calls / visits): every attempt will be made to contact the subject
- Death

Details for the premature termination of the study as a whole (or components thereof) are provided in Section 10 (Premature termination of the study).

For subjects who withdraw from the study prior to the End of Long-term Follow-up visit, the End of Long-term Follow-up visit assessments shall be completed.

In all cases, the reason for withdrawal from the study must be recorded in the electronic case report form (eCRF) and in the source documentation.

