### 3. Study design

#### 3.1 Design overview

*Section modified by Amendments 1 (Section 13.1) and 2 (Sections 13.2.1.1, 13.2.1.2, and 13.2.1.9).*

When eligible, subjects will enter this follow-up study and they, their health care professional, or caregiver will be contacted via telephone (face-to-face data collection is possible and will replace the telephone contact if the subject is on-site within the time window of the planned telephone contact) at 6-month intervals ( $\pm$  28 days) to record:

- Investigator-reported radium-223 dichloride-/placebo-related AEs and related serious adverse events (SAEs);
- All occurrences of leukemia, myelodysplastic syndrome, aplastic anemia, and primary bone cancer or any other new primary malignancy;
- All bone fractures and bone associated events (e.g., osteoporosis), regardless of investigator assessment of causality
- Cancer treatment (including any systemic cytotoxic chemotherapy or radiotherapy for any malignancy; androgen synthesis inhibitors / androgen-receptor antagonists and radiation treatment; excluding analgesics);
- In subjects who receive cytotoxic chemotherapy, all occurrences of febrile neutropenia or hemorrhage during their chemotherapy treatment and for up to 6 months thereafter;
- Survival status.

Subject data collected at other standard-of-care visits and / or contacts may be used to satisfy study-required data. The current study will be terminated at the time the last remaining subject in this study has completed the 7-year follow-up assessment period (or follow-up as defined in the feeder trial protocols) or died.

This study originally was intended to collect long-term follow-up data from prostate cancer studies only; however, radium-223 dichloride is also being studied for other indications. In order to collect comprehensive safety information across all clinical trials with radium-223 dichloride and to allow collection of long-term safety data across indications, subjects with breast cancer and multiple myeloma will also be allowed to enter the long-term follow-up study.

With the currently active feeder trials, approximately 800 subjects are expected to be accrued into this long-term safety follow-up study, but the number of subjects may increase if additional trials feed into this study.

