### 7.5.1.3     Assessments and documentation of adverse events

*Section modified by Amendments 1 (Section 13.1) and 2 (Section 13.2.1.2).*

The investigator has to record on the respective eCRF pages all radium-223 dichloride-/placebo-related AEs ongoing at or occurring from the time of the signing of the ICF and the end of the study. The type of information that should be assessed and recorded by the investigator for each AE is listed in Section 7.5.1.2.

Each event should be described in detail along with start and stop dates (onset and resolution of event), intensity, temporal and causal relationship to feeder trial-related investigational product and / or protocol-related procedures, possible alternative factors (co-morbidities, co-medications), therapeutic action taken, result of therapeutic action, and ultimate outcome of the AE. The investigator's assessment of AEs with grades and causality assessments must be documented and retained in the source documentation.

If more than one radium 223-dichloride- or placebo-related AE occurs, each event should be recorded separately. All AEs and SAEs are to be followed until resolved or as clinically required.

All occurrences of leukemia, myelodysplastic syndrome, aplastic anemia, and primary bone cancer or any other new primary malignancy must be reported as SAEs at any time, and regardless of the investigator's causality assessment. All bone fractures and bone associated events (e.g., osteoporosis) should be collected as either AEs or SAEs if the criteria of SAE were met, regardless of the investigator's causality assessment. If a subject is unable to provide required details for events of interest, this information will need to be obtained from the primary provider.

Adverse events may be reported spontaneously by the subject, the subject's health care professional, or the subject's caregiver, or elicited through questioning during each follow-up telephone call and / or visit during the study. Subject data collected at other standard-of-care visits and / or contacts may be used to satisfy study-required data. As far as possible, all radium-223 dichloride-/placebo-related AEs must be described by their duration (start and stop date), severity (graded according to the NCI-CTCAE, Version 4.03), relationship to treatment, and according to the need of other specific therapy. All information will be recorded in the source documentation and AE eCRF.

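### The withdrawal criteria in Protocol 4.4.1 look only to the participant, while the design accepts a physician or caregiver as the source, so follow-up could end early and unevenly across sites

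*Protocol*

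**What the plan says.** Protocol 4.4.1 has two tiers of withdrawal.

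- **Mandatory** ("Subjects *will* be withdrawn from the study for the following reasons"). One reason is loss to follow-up, defined as "the subject is not able to be contacted for 2 consecutive 6-month interval calls / visits". The stated remedy is "every attempt will be made to contact the subject".
- **Discretionary** ("Subjects *may* be withdrawn from study if the following reason occurs"). Withdrawal is at the sponsor's request in liaison with the investigator, and the examples given are "e.g., obvious non-compliance, inability to provide medical information".

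For anyone who withdraws early, 4.4.1 adds that "the End of Long-term Follow-up visit assessments shall be completed".

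The design sections name more informants. Protocol 3.1 says of participants that "they, their health care professional, or caregiver will be contacted via telephone"; Protocol 7.2.2 and SAP Section 3 name the same three sources. Protocol 7.5.1.3 directs: "If a subject is unable to provide required details for events of interest, this information will need to be obtained from the primary provider". Sections 7.2.2 and 7.2.3 carry the same instruction.

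On analysis, SAP 6.4.2 reports the number and percent of SAF-LTF participants with an event. The version 2 entry in SAP 7.1 records that incidence rates and cumulative incidence were removed. SAP 5.4 imputes nothing except adverse event start dates.

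**The concern.** One situation, a participant who cannot be reached or cannot inform, gets different answers. In Section 7 the site turns to another source. In 4.4.1 it must, or may, end follow-up. The purpose of the study is to detect malignancies and marrow disorders that may appear only years after exposure, so ending follow-up while a permitted source remains gives up the data the study exists to collect.

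The planned analysis does not compensate. A participant closed early stays in the denominator, and events after closure never enter the numerator. If sites read the rule differently, the extent of this also differs by site, and so possibly by feeder trial.

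**Working it through.** **1. The texts side by side.**

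| Situation | Sections 3.1, 7.2.2, 7.2.3, 7.5.1.3 | Section 4.4.1 |
|---|---|---|
| Participant unreachable, physician or caregiver reachable | 3.1 and 7.2.2: contact may be made with the physician or caregiver | Withdrawal mandatory after 2 consecutive failures to reach the participant; no proxy named |
| Participant cannot give details | 7.2.2, 7.2.3 and 7.5.1.3: details to be obtained from the primary provider | Withdrawal possible at the sponsor's request |

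The overview of Amendment 1 suggests how this arose. Its Modification 5 introduced the proxy option and lists the Synopsis, 3.1, 7.2.2 and 7.5.1.3 as affected, but not 4.4.1. The inconsistency rests on the current text; the log only explains it.

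**2. Timing.** Contacts are 6-monthly (±28 days), so the rule is met about 12 months after the last successful contact. The maximum number of contacts is 7 × 2 = 14 for prostate cancer and 5 × 2 = 10 for breast cancer (durations from SAP 5.3).

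**3. Size.** The plan states no loss rate, event rate or power, so there is no figure to reproduce. What follows is an illustration on assumptions.

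- From the documents: N = 800 (approximate, Protocol 3.1) and T = 7 years.
- Assumed: a share f is withdrawn at 3.5 years although a proxy could report; the 7-year risk in everyone else is 10% or 2%; those withdrawn have r times the event rate of the others; hazards are constant; deaths are ignored.
- Hazard L = −ln(1 − risk)/7.
- Complete follow-up: P_full = (1−f)(1−e^(−7L)) + f(1−e^(−7rL)).
- Observed: P_obs = (1−f)(1−e^(−7L)) + f(1−e^(−3.5rL)).

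Example with risk 10%, f = 10%, r = 2. Here e^(−7L) = 0.9, so P_full = 0.9 × 0.10 + 0.1 × (1 − 0.81) = 0.109, and P_obs = 0.9 × 0.10 + 0.1 × (1 − 0.90) = 0.100. The ratio is 0.917, and 800 × 0.009 = 7.2 of 87.2 participants with an event are missed.

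Ratio P_obs/P_full:

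| f | 10% risk: r = 1 / 2 / 3 | 2% risk: r = 1 / 2 / 3 |
|---|---|---|
| 5% | 0.976 / 0.957 / 0.943 | 0.975 / 0.953 / 0.934 |
| 10% | 0.951 / 0.917 / 0.893 | 0.950 / 0.911 / 0.879 |
| 20% | 0.903 / 0.847 / 0.814 | 0.901 / 0.836 / 0.791 |

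The number missed runs from 1.9 of 80.0 to 20.0 of 107.4 at 10% risk, and from 0.4 of 16.0 to 4.6 of 22.2 at 2%.

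Some understatement appears even at r = 1, because a crude percent ignores follow-up time. With a rate per person-year the ratio is 1.000 at r = 1 but 0.876 to 0.979 at r = 2 or 3. A follow-up-adjusted measure would therefore remove the first component but not the second.

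**The case against.** **The rule need not exclude proxies.** It counts interval calls and visits, and Section 7.2.2 lets those be made with the professional or caregiver. A completed call to the oncologist can fairly be read as a completed contact. This stands, and it is why the point is an ambiguity and not a proven exclusion. A mandatory rule with two reasonable readings still invites different practice.

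**The inability example is only discretionary.** This also stands: it needs a sponsor request, and Section 7 points to the provider. The example still names the situation for which Section 7 gives a different answer.

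**Closing assessments limit the loss.** Section 7.2.3 covers related events, malignancies, fractures and survival status, with the provider as back-up. An event that made someone unreachable should be captured there. New malignancies are also reportable at any time, and 7.5.1.4 provides for serious events after the observation period. These points reduce the loss to later events and deaths. None of them creates a scheduled contact after withdrawal.

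**Stronger readings that the documents do not support.**

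- A reader might infer that the sickest participants are lost selectively. That is plausible, but nothing in the documents says who is lost, how many or why.
- A reader might size the problem by the chance of two consecutive missed contacts. With independent misses at an assumed 10% this is 8.0% over 10 contacts and 11.4% over 14; at 20% it is 27.3% and 36.8%. The contact counts are maxima, since follow-up starts at the last feeder dose, may fall partly in the feeder trial and stops at death. Over 4 contacts the figures are 2.8% and 10.4%. They also count personal misses, not withdrawals made while a proxy could report.
- A reader might take non-replacement (4.4.2) to mean the loss is permanent. That section concerns substitution by new subjects. All that can be said is that no re-entry is described.
- A reader might call this informative censoring. With crude percentages and no time-to-event estimate planned, under-ascertainment is the accurate term.

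**Conclusion.** The inconsistency is established on the text: 4.4.1 defines loss on the participant alone and lists inability to inform as a possible reason for withdrawal, while the design accepts proxies and sends the site to the provider. The consequence is conditional. Where 4.4.1 is followed literally, events and deaths after withdrawal are lost although a source remains, and the SAP's crude percentages understate incidence. Where sites count proxy contacts, f is zero and nothing is lost.

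The actual size is unknown. The illustrative range of about 2% to 21% relative understatement rests wholly on the assumed f of 5% to 20%, r of 1 to 3, withdrawal at mid follow-up and no deaths. Confidence is high in the mismatch and low in the amount of bias.

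**What to change.** In Protocol 4.4.1:

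1. Define lost to follow-up as no contact with any of the participant, the treating health care professional or the caregiver at 2 consecutive scheduled contacts, and direct the contact attempts at all three.
2. Limit the inability example to cases where neither a provider nor a caregiver can supply the data.

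This takes a short protocol clarification and a note to sites. No new procedure is needed, since provider and caregiver contact is already in the design. The downside is that some participants stay open longer at sites.

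Allowing follow-up to resume if a source is later re-established is optional and not needed to reconcile the sections. SAP 6.1.1 already tabulates reasons for premature withdrawal by feeder study and treatment group, which will show how many losses were recorded but not how many had a reachable proxy.

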### **Drop-out**

**Drop-out** is defined as a subject who discontinues study participation prematurely for any reason.

### **General procedures**

The subject may object to the generation and processing of post-withdrawal data as specified in Section 11.4.

Any subject removed from the trial will remain under medical supervision until discharge or transfer is medically acceptable.

### **Process for withdrawal of consent**

In order to ensure complete study data, it is specified in the informed consent form (ICF) that the subject agrees to complete follow-up assessments for 7 years in the study (or follow-up as defined in the feeder trial protocols). Only subjects who sign permission to collect this follow-up data should be included in the study.

The subject or his legally acceptable representative can withdraw this initial permission for study participation. In this case, the subject has to expressively inform the investigator (study staff is not sufficient).

### **4.4.2 Replacement**

Withdrawn subjects will not be replaced.

### **4.5 Subject identification**

Each subject will be assigned a new subject number (a unique identification number) for participation in this follow-up study.

The subject number is a 9 digit number consisting of:

Digits 1 to 2 = Country code

Digits 3 to 5 = Center number within the country

(Digits 1 to 5 = Trial unit)

Digits 6 to 9 = Current subject number within the center

The subject was previously enrolled in a selected radium-223 dichloride feeder trial; the site will enter the previous study number and the previous subject number on the Demography page of the eCRF.

## 5. Treatments

### 5.1 Treatments to be administered

No study treatment will be provided in this long-term follow-up study. Subjects received at least 1 dose of radium-223 dichloride or placebo in the selected company-sponsored feeder trials.

### 5.2 Identity of study treatment

Not applicable to this follow-up study.

### 5.3 Treatment assignment

Not applicable to this follow-up study.

### 5.4 Dosage and administration

Not applicable to this follow-up study.

### 5.5 Blinding

Not applicable to this follow-up study.

### 5.6 Drug logistics and accountability

Not applicable to this follow-up study.

### 5.7 Treatment compliance

Not applicable to this follow-up study.

## 6. Non-study therapy

### 6.1 Prior and concomitant therapy

*Section modified by Amendments 1 (Section 13.1) and 2 (Sections 13.2.1.3, 13.2.1.4, 13.2.1.5, and 13.2.1.7).*

Continuation or start of any background therapy and concomitant treatment including as part of a clinical trial is allowed in this follow-up study; however, continuation of feeder trial study drug is not allowed. Radium-223 dichloride should not be given concurrently with abiraterone plus prednisone/prednisolone.

All cancer treatments or medications (including any systemic cytotoxic chemotherapy or radiotherapy for any malignancy; androgen synthesis inhibitors / androgen-receptor antagonists and radiation treatment; excluding analgesics) received during this follow-up study will be recorded. The generic or trade name, indication, dosage, and start and stop dates must be recorded.

Based on the available data on radium-223 dichloride, the option of starting a BHA should be considered, taking into consideration applicable guidelines. Any BHA treatment taken during the study period must be recorded.

## **6.2 Post-study therapy**

Not applicable to this follow-up study.

## 7. Procedures and variables

### 7.1 Tabular schedule of evaluations

*Section modified by Amendments 1 (Section 13.1) and 2 (Section 13.2.1.2, 13.2.1.4, and 13.2.1.9).*

A summary of the schedule of assessments is provided in [Table 7-1](#).

**Table 7-1 Schedule of assessments**

Timing:	Study Enrollment Prior to enrollment	Long-term Follow-up	
		Long-term Follow-up	End of Long-term Follow-up
		Every 6 mos until death a	
Window (days):		± 28	
Eligibility confirmation (check inclusion criteria)	X		
Signing of informed consent form	X		
Radium-223 dichloride-/placebo-related AEs; related SAEs; and occurrence of leukemia, myelodysplastic syndrome, aplastic anemia, and primary bone cancer or any other new primary malignancy.		X b	X b
All bone fractures and bone associated events (e.g., osteoporosis) should be collected as either AEs or SAEs if the criteria of SAE were met, regardless of the investigator's causality assessment.		X b	X b
Subjects who receive cytotoxic chemotherapy will be followed up for the occurrence of febrile neutropenia or hemorrhage during their chemotherapy treatment and for up to 6 months thereafter at a frequency based on local clinical practice		X b	X b
Cancer treatment c		X b	X b
BHA use d		X b	X b
Survival status		X b	X b

Abbreviations: AE = adverse event; BHA = bone health agent; eCRF = electronic case report form; mos = months; SAE = serious adverse event

- a Telephone follow-up every 6 months (± 28 days) for 7 years (or follow-up as defined in the feeder trial protocols) post the last dose of radium-223 dichloride or placebo in the feeder trial or until death. Face-to-face data collection is possible and will replace the telephone contact if the subject is on-site within the time window of the planned telephone contact.
- b It is the clinical site's responsibility to obtain and make available the source documentation for the information collected and to document it in the eCRF.
- c Record any cancer treatments or medications (including any systemic cytotoxic chemotherapy or radiotherapy for any malignancy; androgen synthesis inhibitors / androgen-receptor antagonists and radiation treatment; excluding analgesics).
- d Initiation of BHAs, including bisphosphonates or denosumab, should be considered taking into consideration applicable guidelines. Any BHA treatment taken during the study period must be recorded.

## 7.2 Visit description

### 7.2.1 Study enrollment

The subject must sign the ICF prior to any study-specific assessments (enrollment in the study is defined as the signing of the ICF). Confirmation of eligibility criteria must occur at the time of signing the ICF.

### 7.2.2 Long-term follow-up

*Section modified by Amendments 1 (Section 13.1) and 2 (Section 13.2.1.2, 13.2.1.4, and 13.2.1.9).*

Subjects, their treating health care professional, or caregiver will be contacted by telephone (face-to-face data collection is possible and will replace the telephone contact if the subject is on-site within the time window of the planned telephone contact) every 6 months ( $\pm$  28 days) for 7 years (or follow-up as defined in the feeder trial protocols) following the last radium-223 dichloride or placebo treatment in the feeder trial or until death, to determine the following:

- All radium-223 dichloride-/placebo-related AEs and related SAEs occurring during this period have to be documented and reported. Concomitant treatment associated with these events will not be collected unless it is cancer medication / treatment (including any systemic cytotoxic chemotherapy or radiotherapy for any malignancy; androgen synthesis inhibitors / androgen-receptor antagonists and radiation treatment; excluding analgesics) or new BHA treatment. If a subject is unable to provide required details for events of interest, this information will need to be obtained from the primary provider.
- All occurrences of leukemia, myelodysplastic syndrome, aplastic anemia, primary bone cancer, or any other new primary malignancy must be reported as SAEs at any time and regardless of the investigator's causality assessment.
- All bone fractures and bone associated events (e.g., osteoporosis) should be collected as either AEs or SAEs if the criteria of SAE were met, regardless of the investigator's causality assessment.
- Cancer treatment (including any systemic cytotoxic chemotherapy or radiotherapy for any malignancy; androgen synthesis inhibitors / androgen-receptor antagonists and radiation treatment; excluding analgesics).
- Any BHA treatment taken during the study period must be recorded.
- In subjects who receive cytotoxic chemotherapy, all occurrences of febrile neutropenia or hemorrhage during chemotherapy treatment and for up to 6 months thereafter at a frequency based on local clinical practice.
- Survival status.

Training for conducting the follow-up contacts will be provided to clinical site personnel including, but not limited to, use of a telephone script. Subject data collected at other standard-of-care visits and / or contacts may be used to satisfy study-required data.

It is the clinical site's responsibility to obtain and make available the source documentation for the information collected from the subject and document it in the eCRF.

